### **3.6 Study Timeline**

#### **3.6.1 Primary Completion**

The study is expected to complete accrual at 24 months.

#### **3.6.2 Study Completion**

The study will reach completion 36 months from the time the study opens to accrual.

## 4 Study Drugs

The drugs to be used in this study are outlined below.

### 4.1 Pembrolizumab

Drug Name & Potency	Dosage Form
Pembrolizumab 50 mg	Lyophilized Powder for Injection
Pembrolizumab 100 mg/ 4mL	Solution for Injection

#### 4.1.1 Packaging and Labeling Information

Clinical supplies will be affixed with a clinical label in accordance with regulatory requirements.

#### 4.1.2 Clinical Supplies Disclosure

This trial is open-label; therefore, the subject, the trial site personnel, the Sponsor and/or designee are not blinded to treatment. Drug identity (name, strength) is included in the label text; random code/disclosure envelopes or lists are not provided.

#### 4.1.3 Storage and Handling Requirements

Clinical supplies must be stored in a secure, limited-access location under the storage conditions specified on the label. Receipt and dispensing of trial medication must be recorded by an authorized person at the trial site. Clinical supplies may not be used for any purpose other than that stated in the protocol.

#### 4.1.4 Returns and Reconciliation

The investigator is responsible for keeping accurate records of the clinical supplies received from Merck or designee, the amount dispensed to and returned by the subjects and the amount remaining at the conclusion of the trial.

Upon completion or termination of the study, all unused and/or partially used investigational product will be destroyed at the site per institutional policy. It is the Investigator's responsibility to arrange for disposal of all empty containers, provided that procedures for proper disposal have been established according to applicable federal, state, local and institutional guidelines and procedures, and provided that appropriate records of disposal are kept.

#### 4.1.5 Safety Information

Complete and updated adverse event information for pembrolizumab is available in the Investigational Drug Brochure and/or product package insert.

### 4.2 Ipilimumab

Ipilimumab used in this study will be commercial drug supply. Ipilimumab is to be stored as directed below.

Drug Name & Potency	Dosage Form
Ipilimumab 200 mg (5 mg/mL)	Solution for Injection 40 mL/vial (4 vials/carton)

#### **4.2.1 Packaging and Labeling Information**

Clinical supplies will be affixed with a clinical label in accordance with regulatory requirements.

#### **4.2.2 Clinical Supplies Disclosure**

This trial is open-label; therefore, the subject, the trial site personnel, the Sponsor and/or designee are not blinded to treatment. Drug identity (name, strength) is included in the label text; random code/disclosure envelopes or lists are not provided.

#### **4.2.3 Storage and Handling Requirements**

Clinical supplies must be stored in a secure, limited-access location under the storage conditions specified on the label. Receipt and dispensing of trial medication must be recorded by an authorized person at the trial site. Store at 2° - 8°C. Protect from light and freezing.

Clinical supplies may not be used for any purpose other than that stated in the protocol.

- Do not shake product.
- Inspect parenteral drug products visually for particulate matter and discoloration prior to administration. Discard vial if solution is cloudy, there is pronounced discoloration (solution may have pale-yellow color), or there is foreign particulate matter other than translucent-to-white, amorphous particles.

#### Preparation of Solution

- Allow the vials to stand at room temperature for approximately 5 minutes prior to preparation of infusion.
- Withdraw the required volume of ipilimumab and transfer into an intravenous bag.
- Dilute with 0.9% Sodium Chloride Injection, USP or 5% Dextrose Injection, USP to prepare a diluted solution with a final concentration ranging from 1 mg/mL to 2 mg/mL. Mix diluted solution by gentle inversion.
- Store the diluted solution for no more than 24 hours under refrigeration (2°C to 8°C, 36°F to 46°F) or at room temperature (20°C to 25°C, 68°F to 77°F).
- Flush the intravenous line with 0.9% Sodium Chloride Injection, USP or 5% Dextrose Injection, USP after each dose.

#### **4.2.4 Returns and Reconciliation**

#### **4.2.5 Safety Information**

##### WARNINGS AND PRECAUTIONS

Ipilimumab can result in severe and fatal immune-mediated reactions [see Boxed Warning].

##### **Immune-Mediated Enterocolitis**

Immune-mediated enterocolitis, including fatal cases, can occur with ipilimumab.

Monitor patients for signs and symptoms of enterocolitis (such as diarrhea, abdominal pain, mucus or blood in stool, with or without fever) and of bowel perforation (such as peritoneal signs and ileus). In symptomatic patients, rule out infectious etiologies and consider endoscopic evaluation for persistent or severe symptoms.

Permanently discontinue ipilimumab in patients with severe enterocolitis and initiate systemic corticosteroids at a dose of 1 to 2 mg/kg/day of prednisone or equivalent. Upon improvement to Grade 1 or less, initiate corticosteroid taper and continue to taper over at least 1 month. In clinical trials, rapid corticosteroid tapering resulted in recurrence or worsening symptoms of enterocolitis in some patients. Consider adding anti-TNF or other immunosuppressant agents for management of immune-mediated enterocolitis unresponsive to systemic corticosteroids within 3 to 5 days or recurring after symptom improvement.

Withhold ipilimumab dosing for moderate enterocolitis; administer anti-diarrheal treatment and, if persistent for more than 1 week, initiate systemic corticosteroids at a dose of 0.5 mg/kg/day prednisone or equivalent.

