#### Metastatic Melanoma

In patients receiving ipilimumab 3 mg/kg in Trial 1, severe, life-threatening, or fatal (diarrhea of 7 or more stools above baseline, fever, ileus, peritoneal signs; Grade 3 to 5) immune-mediated enterocolitis occurred in 34 ipilimumab-treated patients (7%), and moderate (diarrhea with up to 6 stools above baseline, abdominal pain, mucus or blood in stool; Grade 2) enterocolitis occurred in 28 ipilimumab -treated patients (5%). Across all ipilimumab-treated patients (n=511), 5 patients (1%) developed intestinal perforation, 4 patients (0.8%) died as a result of complications, and 26 patients (5%) were hospitalized for severe enterocolitis.

The median time to onset of Grade 3 to 5 enterocolitis was 1.7 months (range: 11 days to 3.1 months) and for Grade 2 enterocolitis was 1.4 months (range: 2 days to 4.3 months).

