### Immune-Mediated Endocrinopathies

Immune-mediated endocrinopathies, including life-threatening cases, can occur with ipilimumab.

Monitor patients for clinical signs and symptoms of hypophysitis, adrenal insufficiency (including adrenal crisis), and hyper- or hypothyroidism. Patients may present with fatigue, headache, mental status changes, abdominal pain, unusual bowel habits, and hypotension, or nonspecific symptoms which may resemble other causes such as brain metastasis or underlying disease. Unless an alternate etiology has been identified, signs or symptoms of endocrinopathies should be considered immune-mediated.

Monitor clinical chemistries, adrenocorticotrophic hormone (ACTH) level, and thyroid function tests at the start of treatment, before each dose, and as clinically indicated based on symptoms. In a limited number of patients, hypophysitis was diagnosed by imaging studies through enlargement of the pituitary gland.

Withhold ipilimumab dosing in symptomatic patients and consider referral to an endocrinologist. Initiate systemic corticosteroids at a dose of 1 to 2 mg/kg/day of prednisone or equivalent, and initiate appropriate hormone replacement therapy [see Dosage and Administration (2.3)].

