Diarrhea / Colitis	Grade 2 or 3	Withhold	
 
• Administer corticosteroids (initial dose of 1-2 mg/kg prednisone or equivalent) followed by taper
 
	
 
• Monitor participants for signs and symptoms of enterocolitis (ie, diarrhea, abdominal pain, blood or mucus in stool with or without fever) and of bowel perforation (ie, peritoneal signs and ileus).
 
• Participants with <math>\geq</math> Grade 2 diarrhea suspecting colitis should consider GI consultation and performing endoscopy to rule out colitis.
 
• Participants with diarrhea/colitis should be advised to drink liberal quantities of clear fluids. If sufficient oral fluid intake is not feasible, fluid and electrolytes should be substituted via IV infusion.
 

	Grade 4	Permanently discontinue		
AST / ALT elevation or Increased bilirubin	Grade 2	Withhold	
 
• Administer corticosteroids (initial dose of 0.5- 1 mg/kg prednisone or equivalent) followed by taper
 
	
 
• Monitor with liver function tests (consider weekly or more frequently until liver enzyme value returned to baseline or is stable)
 

	Grade 3 or 4	Permanently discontinue	
 
• Administer corticosteroids (initial dose of 1-2 mg/kg prednisone or equivalent) followed by taper
 
	

Type 1 diabetes mellitus (T1DM) or Hyperglycemia	Newly onset T1DM or Grade 3 or 4 hyperglycemia associated with evidence of $\beta$ -cell failure	Withhold	
 
Initiate insulin replacement therapy for participants with T1DM
 
Administer anti-hyperglycemic in participants with hyperglycemia
 
	
 
Monitor participants for hyperglycemia or other signs and symptoms of diabetes.
 

Hypophysitis	Grade 2	Withhold	
 
Administer corticosteroids and initiate hormonal replacements as clinically indicated.
 
	
 
Monitor for signs and symptoms of hypophysitis (including hypopituitarism and adrenal insufficiency)
 

	Grade 3 or 4	Withhold or permanently discontinue 		

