**Table 3 Ipilimumab Dose Modification Guidelines for Drug-Related Adverse Events**

Toxicity	Hold For Grade	Timing for Restarting Treatment	Treatment Discontinuation
Diarrhea/Colitis	2	Toxicity resolves to Grade 0-1	Toxicity does not resolve within 12 weeks of last dose or inability to reduce corticosteroid to 10 mg or less of prednisone or equivalent per day within 12 weeks. Patients are to be treated with 1 mg/kg prednisone or equivalent if grade 2 or greater toxicity and tapered over several weeks
	3-4	Permanently discontinue	Permanently discontinue
AST, ALT, or Increased Bilirubin	2	Toxicity resolves to Grade 0-1	Toxicity does not resolve within 12 weeks of last dose
	3-4	Permanently discontinue (see exception below) a	Permanently discontinue
Type 1 diabetes mellitus (if new onset) or Hyperglycemia	T1DM or 3-4	Hold ipilimumab for new onset Type 1 diabetes mellitus or Grade 3-4 hyperglycemia associated with evidence of beta cell failure	Discontinue permanently
Hypophysitis	2-4	Toxicity resolves to Grade 0-1. Therapy with pembrolizumab can be continued while endocrine replacement therapy is instituted	Toxicity does not resolve within 12 weeks of last dose or inability to reduce corticosteroid to 10 mg or less of prednisone or equivalent per day within 12 weeks
Hyperthyroidism	3	Toxicity resolves to Grade 0-1	Toxicity does not resolve within 12 weeks of last dose or inability to reduce corticosteroid to 10 mg or less of prednisone or equivalent per day within 12 weeks
	4	Permanently discontinue	Permanently discontinue
Hypothyroidism		Therapy with ipilimumab can be continued while thyroid replacement therapy is instituted	Therapy with ipilimumab can be continued while thyroid replacement therapy is instituted
Infusion Reaction	2 b	Toxicity resolves to Grade 0-1	Permanently discontinue if toxicity develops despite adequate premedication
	3-4	Permanently discontinue	Permanently discontinue
Pneumonitis	2	Toxicity resolves to Grade 0-1	Toxicity does not resolve within 12 weeks of last dose or inability to reduce corticosteroid to 10 mg or less of prednisone or equivalent per day within 12 weeks
	3-4	Permanently discontinue	Permanently discontinue
Renal Failure or Nephritis	2	Toxicity resolves to Grade 0-1	Toxicity does not resolve within 12 weeks of last dose or inability to reduce corticosteroid to 10 mg or less of prednisone or equivalent per day within 12 weeks
	3-4	Permanently discontinue	Permanently discontinue

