## 5.4 Rescue Medications & Supportive Care

### 5.4.1 Supportive Care Guidelines

Subjects should receive appropriate supportive care measures as deemed necessary by the treating investigator. Suggested supportive care measures for the management of adverse events with potential immunologic etiology are outlined below. Where appropriate, these guidelines include the use of oral or intravenous treatment with corticosteroids as well as additional anti-inflammatory agents if symptoms do not improve with administration of corticosteroids. Note that several courses of steroid tapering may be necessary as symptoms may worsen when the steroid dose is decreased. For each disorder, attempts should be made to rule out other causes such as metastatic disease or bacterial or viral infection, which might require additional supportive care. The treatment guidelines are intended to be applied when the investigator determines the events to be related to pembrolizumab.

Note: if after the evaluation the event is determined not to be related, the investigator does not need to follow the treatment guidance (as outlined below). Refer to Section 5.3 for dose modification.

It may be necessary to perform conditional procedures such as bronchoscopy, endoscopy, or skin photography as part of evaluation of the event.

- **Pneumonitis:**
  - For **Grade 2 events**, treat with systemic corticosteroids. When symptoms improve to Grade 1 or less, steroid taper should be started and continued over no less than 4 weeks.
  - For **Grade 3-4 events**, immediately treat with intravenous steroids. Administer additional anti-inflammatory measures, as needed.
  - Add prophylactic antibiotics for opportunistic infections in the case of prolonged steroid administration.
- **Diarrhea/Colitis:** Subjects should be carefully monitored for signs and symptoms of enterocolitis (such as diarrhea, abdominal pain, blood or mucus in stool, with or without fever) and of bowel perforation (such as peritoneal signs and ileus).
  - All subjects who experience diarrhea/colitis should be advised to drink liberal quantities of clear fluids. If sufficient oral fluid intake is not feasible, fluid and electrolytes should be substituted via IV infusion. For Grade 2 or higher diarrhea, consider GI consultation and endoscopy to confirm or rule out colitis.
  - For **Grade 2 diarrhea/colitis**, administer oral corticosteroids.

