  - For **Grade 3 or 4 diarrhea/colitis**, treat with intravenous steroids followed by high dose oral steroids.
  - When symptoms improve to Grade 1 or less, steroid taper should be started and continued over no less than 4 weeks.
- **Type 1 diabetes mellitus (if new onset, including diabetic ketoacidosis [DKA]) or ≥ Grade 3 Hyperglycemia, if associated with ketosis (ketonuria) or metabolic acidosis (DKA)**
  - For **T1DM or Grade 3-4 Hyperglycemia**
    - Insulin replacement therapy is recommended for Type I diabetes mellitus and for Grade 3-4 hyperglycemia associated with metabolic acidosis or ketonuria.
    - Evaluate patients with serum glucose and a metabolic panel, urine ketones, glycosylated hemoglobin, and C-peptide.
- **Hypophysitis:**
  - For **Grade 2 events**, treat with corticosteroids. When symptoms improve to Grade 1 or less, steroid taper should be started and continued over no less than 4 weeks. Replacement of appropriate hormones may be required as the steroid dose is tapered.
  - For **Grade 3-4 events**, treat with an initial dose of IV corticosteroids followed by oral corticosteroids. When symptoms improve to Grade 1 or less, steroid taper should be started and continued over no less than 4 weeks. Replacement of appropriate hormones may be required as the steroid dose is tapered.
- **Hyperthyroidism or Hypothyroidism:** Thyroid disorders can occur at any time during treatment. Monitor patients for changes in thyroid function (at the start of treatment, periodically during treatment, and as indicated based on clinical evaluation) and for clinical signs and symptoms of thyroid disorders.

- **Grade 2** hyperthyroidism events (and **Grade 2-4** hypothyroidism):
  - In hyperthyroidism, non-selective beta-blockers (e.g. propranolol) are suggested as initial therapy.
  - In hypothyroidism, thyroid hormone replacement therapy, with levothyroxine or liothyroinine, is indicated per standard of care.
- **Grade 3-4** hyperthyroidism
  - Treat with an initial dose of IV corticosteroid followed by oral corticosteroids. When symptoms improve to Grade 1 or less, steroid taper should be started and continued over no less than 4 weeks. Replacement of appropriate hormones may be required as the steroid dose is tapered.
- **Hepatic:**
  - For **Grade 2** events, monitor liver function tests more frequently until returned to baseline values (consider weekly).
    - Treat with IV or oral corticosteroids

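### For Grade 2 diarrhea/colitis, Section 4.2.5 and the Treatment Plan (Section 5) give different steroid start times and first doses; a smaller conflict affects some thyroid events, and no text says which governs

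*Combined protocol and SAP*

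**What the plan says.** **Grade 2 diarrhea/colitis.** Four places in the combined protocol and SAP address it.

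- Section 4.2.5 (Immune-Mediated Enterocolitis) withholds ipilimumab for moderate events and begins with anti-diarrheal treatment; then, "if persistent for more than 1 week, initiate systemic corticosteroids at a dose of 0.5 mg/kg/day prednisone or equivalent". The incidence paragraph that follows shows that moderate means Grade 2: "moderate (diarrhea with up to 6 stools above baseline, abdominal pain, mucus or blood in stool; Grade 2".
- Table 3 (5.3.2, ipilimumab): "Patients are to be treated with 1 mg/kg prednisone or equivalent if grade 2 or greater toxicity and tapered over several weeks".
- Table 2 (5.3.1, pembrolizumab), for Grade 2 or 3: "Administer corticosteroids (initial dose of 1-2 mg/kg prednisone or equivalent) followed by taper". Its general instructions set a taper of at least 4 weeks.
- Section 5.4.1, for Grade 2: "administer oral corticosteroids", with no dose and no waiting period. Its scope is stated as follows: "The treatment guidelines are intended to be applied when the investigator determines the events to be related to pembrolizumab".

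**Thyroid events.** Section 4.2.5 (Immune-Mediated Endocrinopathies) names hyper- and hypothyroidism among the conditions to monitor. Its management paragraph withholds ipilimumab in symptomatic patients and continues: "Initiate systemic corticosteroids at a dose of 1 to 2 mg/kg/day of prednisone or equivalent, and initiate appropriate hormone replacement therapy". Table 2 lists beta-blockers or thionamides for hyperthyroidism and thyroid hormone for Grade 2-4 hypothyroidism, with no steroid named. Section 5.4.1 suggests beta-blockers for Grade 2 hyperthyroidism and says "In hypothyroidism, thyroid hormone replacement therapy, with levothyroxine or liothyroinine, is indicated per standard of care". Table 3 allows ipilimumab to continue in hypothyroidism.

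**Regimen.** Table 1 gives both antibodies on Day 1 of each 3-week cycle for cycles 1-4.

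**The concern.** A patient with Grade 2 colitis during cycles 1-4 falls under all of these texts at once. An investigator who follows 4.2.5 waits more than a week and then starts at the lower dose. One who follows Table 2 or Table 3 starts without waiting and at a higher dose. Each is following the protocol as written.

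Two things are at stake. The first is patient safety: 4.2.5 itself reports perforations and deaths from enterocolitis on ipilimumab. The second is interpretation: toxicity is a secondary endpoint (2.3.2), and its course is harder to describe if first-line management depends on which page was consulted. Nothing here touches the response endpoint, the sample size or the test.

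**Working it through.** The plan gives no figure on this point to reproduce, so the check is a comparison of texts plus simple dose arithmetic.

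**Step 1. Grade 2 colitis side by side.**

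| Text | Written for | Waiting period | First dose (prednisone or equivalent) | Taper |
|---|---|---|---|---|
| 4.2.5 | ipilimumab | more than 1 week | 0.5 mg/kg/day | none stated for moderate events |
| Table 3 | ipilimumab | none | 1 mg/kg | several weeks |
| Table 2 | pembrolizumab | none | 1-2 mg/kg | at least 4 weeks |
| 5.4.1 | pembrolizumab-related events | none | none stated | at least 4 weeks |

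**Step 2. Ratio of first doses.** Tables 2 and 3 do not state a time unit; I read them as per day. Body weight cancels, so no weight assumption is needed:

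- Table 3 to 4.2.5: 1 / 0.5 = 2.
- Table 2 to 4.2.5: 1 / 0.5 = 2 up to 2 / 0.5 = 4.

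**Step 3. Illustration in mg/day.** The documents give no body weight. For an assumed 80 kg:

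- 4.2.5: 80 x 0.5 = 40 mg/day.
- Table 3: 80 x 1 = 80 mg/day.
- Table 2: 80 x 1 to 80 x 2 = 80 to 160 mg/day.

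Over an assumed 50 to 100 kg, the first dose is 25-50 mg/day at 0.5 mg/kg, 50-100 mg/day at 1 mg/kg and 100-200 mg/day at 2 mg/kg.

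**Step 4. Does each drug having its own text resolve it?** No. Section 4.2.5 and Table 3 both concern ipilimumab and disagree with each other. Section 5.4.1 limits itself to events attributed to pembrolizumab but gives no way to attribute colitis when both antibodies are on board. In the ipilimumab trial described in 4.2.5, median onset of Grade 2 enterocolitis was 1.4 months, about 6 weeks (1.4 x 30.4 / 7 = 6.1). That lies within the 4 x 3 = 12 weeks of combined treatment.

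**Step 5. How many patients?** The only rate given is 28 of 511 on ipilimumab 3 mg/kg alone: 28 / 511 = 5.5%, and 0.055 x 43 = 2.4, or about 2 patients. This trial uses 1 mg/kg with pembrolizumab and aspirin. Its Grade 2 colitis rate is not given, so this count is illustrative only.

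**Step 6. Thyroid events side by side.**

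| Event | 4.2.5, if symptomatic | Table 2 and 5.4.1 | Conflict on steroid start? |
|---|---|---|---|
| Hypothyroidism (Grade 2-4) | steroids 1-2 mg/kg/day plus hormone replacement | hormone replacement, no steroid named | yes |
| Hyperthyroidism, Grade 2 | the same paragraph | no steroid named | yes |
| Hyperthyroidism, Grade 3-4 | the same paragraph | 5.4.1: IV then oral steroids | not between 4.2.5 and 5.4.1 |

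For hypothyroidism there is a further difference: 4.2.5 withholds ipilimumab in symptomatic patients, while Table 3 lets it continue.

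**The case against.** **Section 4.2.5 reads like imported product labelling.** It points to a boxed warning and to numbered sections on dosing and specific populations that do not correspond to this protocol, where 2.3 is Endpoints. It sits under Study Drugs, whereas Section 5 is the Treatment Plan. An experienced site might well treat it as background. This makes the conflict less likely to reach a patient but does not remove it: the text is written as instruction, and nothing calls it background or sets an order of precedence.

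**The Section 5 texts agree with one another.** A reader might infer that the colitis rule is stated three incompatible ways. It is not. The 1 mg/kg in Table 3 lies inside the range in Table 2, a taper over several weeks is compatible with at least 4 weeks, and 5.4.1 adds oral steroids without a dose. All three can be met at once, so the conflict is 4.2.5 against Section 5. (This observes that the texts overlap; it is not a view on which dose is right.)

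**The thyroid paragraph is generic.** It covers hypophysitis, adrenal insufficiency and thyroid disease together, so its authors may not have meant steroids for every thyroid event. That is fair and makes this limb secondary. As written, though, it draws no distinction among them.

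**Section 5.4.1 offers its measures as suggestions, subject to the treating investigator's judgment.** That holds for 5.4.1, but Tables 2 and 3 and 4.2.5 are worded as directions.

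**Conclusion.** The concern holds for Grade 2 diarrhea/colitis. Section 4.2.5 differs from Tables 2 and 3 by a factor of 2 to 4 in first dose and by more than a week in start, with no rule of precedence. The ratio holds at any body weight, given the per-day reading of the tables; the mg/day figures assume 80 kg, and the count of about 2 of 43 is borrowed from a different dose and regimen. A secondary conflict holds for symptomatic hypothyroidism and symptomatic Grade 2 hyperthyroidism only. It should not be extended to all thyroid events, because 5.4.1 also gives steroids for Grade 3-4 hyperthyroidism.

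A reader might also infer that the choice of starting dose changes who is permanently taken off ipilimumab, since Table 3 stops it when prednisone cannot be brought to 10 mg/day or less within 12 weeks. The documents do not support that. The colitis entry in Table 3 states its own 1 mg/kg start beside that criterion, so another start arises only if a site departs from the entry. Ipilimumab is also confined to cycles 1-4: on schedule the fourth dose falls 3 x 3 = 9 weeks after the first, so 12 weeks from even the first dose already lies beyond it. Nor does Table 3 have a steroid-based stop for hypothyroidism.

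This is an inconsistency of text that should be corrected for patient safety and uniform toxicity management. It does not alter the statistical design.

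**What to change.** Reconcile 4.2.5 (enterocolitis and endocrinopathies), Table 2 with its general instructions, Table 3 and 5.4.1. Each grade of diarrhea/colitis, hypothyroidism and hyperthyroidism should carry one instruction on when steroids start, the first dose with its time unit, and the taper. For hypothyroidism, also reconcile whether ipilimumab is withheld or continued. Add one sentence naming the section that governs if texts differ, and say how it applies to events in cycles 1-4 that cannot be attributed to one antibody.

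Which rule applies and which section governs are for the sponsor's clinicians. Declaring 4.2.5 to be background would itself select one of the conflicting rules, so that step should be their explicit decision and not an editorial one.

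The cost is protocol wording in one amendment, with no added visits, tests or patients.
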